# 5.6. Other Considerations for Data Analyses and Data Handling Conventions

Other considerations for data analyses and data handling conventions are outlined in the appendices:

Section	Component
9.3	Appendix 3: Assessment Windows
9.4	Appendix 4: Study Phases and Treatment Emergent Adverse Events
9.5	Appendix 5: Data Display Standards & Handling Conventions
9.6	Appendix 6: Derived and Transformed Data
9.7	Appendix 7: Reporting Standards for Missing Data

### 6. STUDY POPULATION ANALYSES

## 6.1. Overview of Planned Study Population Analyses

The study population analyses will be based on the Safety population unless otherwise stated.

Study population analyses including analyses of subject's disposition, protocol deviations, demographic and baseline characteristics, prior and concomitant medications, exposure and treatment compliance will be based on GSK Core Data Standards. Details of the planned displays are presented in Appendix 12: List of Data Displays.

## 6.1.1. Study Populations

The number of subjects randomised and the number of subjects who were in the mITT and Safety population will be presented by treatment group and overall.

The number of subjects in the ASE population, the number and percentage of subjects who were screening and run-in failures, and who had exacerbations during the run-in period will be presented. In addition, the reasons for screening failures will also be provided.

The number and percentage of subjects who completed the study, who withdrew prematurely from the study and who reported each primary and sub-reason for withdrawal will be presented for each treatment group and overall. Similarly, tables of demography and baseline characteristics will be produced by treatment group and overall.

If any sites were closed due to audit findings, failures to adhere to GCP or any other findings, an additional 'Safety excluding closed sites' population will be added to all study population tables, or in the case of demography and baseline characteristic tables a repeat table for this population will be produced. If no sites were closed, this information will be included in the footnote and no additional tables will be provided.

#### 6.2. Medical Conditions

The number and percentage of subjects reporting each current medical condition specified in the eCRF will be presented by randomised treatment group and overall. All medical conditions must be summarised on this table regardless of frequency, and will be repeated for current and past medical conditions.

A separate table of 'Cardiovascular Risk Factors' will also be produced. This will summarise the number and percentages of subjects with the following current or past medical conditions: Arrhythmia, Cerebrovascular Accident, Congestive Heart Failure, Coronary Artery Disease, Diabetes Mellitus, Hypertension, Hypercholesterolemia, Myocardial Infarction.

#### 6.3. Concomitant Medications

Medications categorised as 'Other medications' will include medications not used to treat COPD or low bone mineral density [BMD] and will be summarised by Anatomical-Therapeutic-Chemical (ATC) level 1 and ingredient. COPD medications not given for an exacerbation will be summarised by Respiratory Medication Class (RMC). COPD medications given for exacerbations whilst on treatment will also be summarised by RMC. Multi-ingredient medications will be presented according to their combination ATC classification rather than the classifications of the individual ingredients.

BMD medications, taken to improve bone mineral density, will be summarised by treatment group and overall. Bone mineral density medications will be identified using ATC codes along with reviewing all concomitant medications prior to database freeze to ensure all relevant medications are included.

COPD, BMD and Other medications will be listed separately. The COPD medications listing will indicate whether each medication was taken for an exacerbation. Listings will indicate in which study phases each medication was taken (pre-treatment and/or on-treatment and/or post-treatment).

A listing of the relationship between ATC Level 1, ingredient and verbatim text will be produced for 'Other medications' only.

## 6.4. Screening Results

Screening (which will be baseline) bone mineral density results at both total hip and lumbar spine (L1-L4) will be summarised overall and by gender according to treatment.

Pre- and post-bronchodilator FEV1, FVC, FEV1/FVC ratio, post-bronchodilator FEV1 percentage of predicted normal and FEV1 reversibility to bronchodilator (expressed in mL and as a percentage of post-bronchodilator and grouped into the following categories: "<12% or <200mL" " $\geq$ 12% and  $\geq$ 200mL"; reversibility will also be expressed also as a percentage of predicted) at screening (see Section 5.2) will be summarised by treatment group and overall. At randomisation FEV1, FVC and FEV1/FVC will be summarised by treatment group and overall.

## 7. SAFETY ANALYSES

## 7.1. Primary Safety Analyses

Due to the known variability between sites and scanners, prior to the end of the study each machine has a phantom scanned. This phantom is a standardised bone image with a set density. As the true density of the phantom is known, it means that the difference between the true value and the machine value can be calculated, this is known as the correction factor

Throughout the reporting of this study, all summaries and analysis of bone mineral density will use the corrected bone mineral density values only as these can be considered as standardised values where machine variability had been accounted for.

It is also important to highlight that if a subject was affected by a hip fracture during the study then the other native hip was used for all subsequent BMD assessments.

### 7.1.1. Endpoint / Variables

Bone mineral density measured at the Total Hip

## 7.1.2. Summary Measure

Percentage change from baseline per annum

## 7.1.3. Population of Interest

The primary safety analyses will be based on the Safety populations, unless otherwise specified. In the instance that all subjects are assigned their randomised treatment for at least 50% of the treatment period, the Safety population will be identical to the mITT.

## 7.1.4. Strategy for Intercurrent (Post-Randomisation) Events

The four key intercurrent events in this study are;

- Use of concomitant medication taken to increase a subject's bone mineral density (which we will term "BMD medication")
- Use of systemic corticosteroids (SCS) which may decrease a subject's BMD
- Temporary discontinuation of investigational product
- Permanent discontinuation of IP.

The primary aim of this study is to generate the 'while on treatment' estimand of the difference in percentage change from baseline per annum between FF/VI  $\pm$  BMD medication/SCS and VI  $\pm$  BMD medication/SCS.

Therefore, after a subject takes BMD medication or SCS, or temporarily discontinues IP, BMD will continue to be collected, and this data will be used in the analysis.

However, once a subject has permanently discontinued IP their inhaled therapy may be switched, and so data after this event will no longer reflect the treatment comparison of

interest. As this is a non-inferiority study, focusing on safety not efficacy, BMD data collected after this event will not be used in the analysis.

Intermittent missing data not due to an intercurrent event, e.g. sporadic missing of a visit, will not be explicitly imputed and will be treated as missing at random. Subsequent data collected will be included in the analysis.

## 7.1.5. Statistical Analyses / Methods

Details of the planned displays are provided in Appendix 12: List of Data Displays and will be based on GSK data standards and statistical principles.

Unless otherwise specified, endpoints / variables defined in Section 7.1.1 will be summarised using descriptive statistics, graphically presented (where appropriate) and listed.

### 7.1.5.1. Statistical Methodology Specification

#### Endpoint(s)

Bone mineral density measured at the total hip

#### **Model Specification**

#### Model:

[figure not shown]
- The ratio of post-baseline BMD values to baseline BMD values will be log transformed prior to analysis. Note: Log(post baseline BMD/baseline BMD) is equivalent to log(post baseline BMD)

   log(baseline BMD).
- A repeated measures model with terms for treatment, visit, visit by treatment, the logarithm of baseline BMD, the logarithm of baseline BMD by visit, baseline BMI (continuous), age (continuous) and gender will be fitted.
- This will make the analysis model: log(post baseline BMD/baseline BMD)= treatment + visit + visit\*treatment + log(baseline BMD) + log(baseline BMD)\*visit + BMI + age + gender
- The difference between FF/VI and VI will be calculated using the log estimate for FF/VI the log estimate for VI.

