5.6. Concomitant Medications and Non-Drug Therapies

All COPD medications taken within 30 days prior to Visit 0 and during the run-in period will be recorded in the eCRF. All COPD and non-COPD concomitant medications taken during the study will be recorded in the eCRF. The minimum requirement includes, but is not limited to name of the medications, and the dates of the administration.

Note: Care is advised when co-administering with strong CYP 3A4 inhibitors (e.g. ketoconazole, ritonavir) as there is potential for an increased systemic exposure to both fluticasone furoate and vilanterol, which could lead to an increase in the potential for adverse reactions.

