8.3.3. Treatment Comparisons

8.3.3.1. Primary Comparisons of Interest

BMD measured for the total hip will be summarized by visit and as change from baseline at each visit for raw values, percent changes from baseline, t-scores, and z-scores. The percent change from baseline in BMD for the total hip will be the primary endpoint, and analyzed using a repeated measures model with terms for treatment, time, time by treatment, baseline BMD, baseline BMI and gender. Contrasts will be formed using the time by treatment variable to provide 95% confidence intervals for the treatment difference with the unit of percent change per year. The 95% confidence interval will be compared to a lower bound of -1%/year in order to assess clinical non-inferiority. Any

additional covariates for the model, along with other details, including model inclusion and exclusion criteria for those covariates, will be determined a priori in a detailed Reporting and Analysis Plan (RAP) that will be completed prior to unblinding of the study.

The percent change from baseline in BMD at the L1-L4 region of the spine will also by summarized and analyzed in the same manner as the BMD data for the total hip.

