## 5.4. Examination of Covariates, Other Strata and Subgroups

#### 5.4.1. Covariates and Other Strata

The list of covariates and other strata may be used in descriptive summaries and statistical analyses, some of which may also be used for subgroup analyses. Additional covariates and other strata of clinical interest may also be considered.

Category	Details
Covariates:	Age, Gender, Baseline BMD, Visit, Baseline BMI
All models	
Covariates:	Treatment*covariate interactions will be included in the model, and if these are
To be investigated	significant (10% level) then a split model will be investigated.

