## 5.4.2. Examination of Subgroups

The analysis of bone mineral density will be presented overall and by gender (males and females). For the gender analysis, each individual gender will have its own separate model fitted excluding any data from the opposite gender (split model).

There are no other planned subgroup analyses unless the treatment\*covariate interaction is shown to be significant at the 10% level, in which case subgroups will be calculated and presented in the same way as gender. For example, if smoking status was shown to be significant it would be categorised as demonstrated below and then presented by these categories.

Table 3 shows all potential subgroups that will be investigated.

Table 3	Potential	Subgroups
Iddie	i Otelitiai	Oubgioups

Covariate	Categorical or Continuous
Age	Continuous
Baseline BMI	BMI will be modelled as continuous but if it needs to be categorised for the purposes of producing summaries by subgroups the following categories will be used; < 25, 25 <= to < 30 and >= 30. This is based on the WHO definition for categorising BMI but combining the < 18.5 and 18.5 <= to <25 categories due to low number of subjects in the HZC102972 study having a BMI < 18.5.
Smoking Status	Categorical: Current or Former.

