#### Covariates to be investigated:

 Treatment\*Covariate interactions will be included in the model individually. If these are significant at the 10% level then a model split by the covariate of interest will be investigated.

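### The BMD models leave out smoking status and recent inhaled-steroid use, both recorded before randomisation; adding them is an optional, small precision gain, not a correction of bias

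*SAP*

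**What the plan says.** SAP 7.1.5.1 gives the primary model: treatment, visit, their interaction, log baseline BMD and its interaction with visit, and then "baseline BMI (continuous), age (continuous) and gender will be fitted". SAP 5.4.1 gives the covariates for all models as "Age, Gender, Baseline BMD, Visit, Baseline BMI". SAP 7.2.5.1 carries the same specification to the spine and to the by-gender analyses, where each gender has its own model.

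Smoking status appears in SAP 5.4.2, Table 3, as a potential subgroup with the levels current and former: "if smoking status was shown to be significant it would be categorised as demonstrated below". The route there is a treatment-by-covariate test at the 10% level, and SAP 7.1.5.1 says these "interactions will be included in the model individually". That step is separate from the estimate used for the non-inferiority test.

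On what is collected, the protocol's Time and Events Table has smoking history and status from Visit 1. Protocol 5.6 states: "All COPD medications taken within 30 days prior to Visit 0 and during the run-in period will be recorded in the eCRF". For non-COPD drugs the same section covers use during the study and gives no look-back. SAP 6.3 says "BMD medications, taken to improve bone mineral density, will be summarised by treatment group and overall", and Listing 37 in SAP 9.9.9 splits those medications into pre-, on- and post-treatment.

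On further covariates, Protocol 8.3.3.1 says that any "additional covariates for the model, along with other details, including model inclusion and exclusion criteria for those covariates, will be determined a priori" in the RAP. SAP 5.4.1 says instead: "Additional covariates and other strata of clinical interest may also be considered". It names none.

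**The concern.** Randomisation is stratified by gender only, so other baseline factors are balanced only by chance. Adjusting for a baseline factor that predicts BMD change removes that noise and narrows the interval compared with −1 %/year. The SAP itself thinks smoking status worth examining in relation to BMD, and the effect of inhaled steroids on bone is the reason for the trial. Both have recorded baseline values, yet neither is in the model that produces the primary or key secondary result.

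What is at stake is precision. It matters least for the combined hip analysis, which has ample power, and most for the by-gender analyses, which were sized at 80% with almost nothing to spare.

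**Working it through.** **Inputs from the documents.** Margin −1 %/year, true difference −0.3 %/year, SD 1.3 %/year and a two-sided 95% interval (SAP 2.5). There are 56 evaluable subjects per gender per arm (Protocol 8.2.1), hence 112 per arm combined. The distance to the margin is 1 − 0.3 = 0.7 %/year.

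**Input not in the documents.** R², the share of residual variance that the added factors explain beyond the present model. It is an assumption: 0.02 to 0.10, with 0.20 as an outer case.

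**Reproducing the plan's figures.** Power = Φ(0.7 / SE − 1.96), with SE = SD × √(2/n).

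- Combined: SE = 1.3 × √(2/112) = 0.174; 0.7/0.174 − 1.96 ≈ 2.07; power 98.1%. SAP Table 2 states 98%. The other eight cells of that table also reproduce at 112 per arm.
- Per gender: SE = 1.3 × √(2/56) = 0.246; 0.7/0.246 − 1.96 ≈ 0.89; power 81.3%. The t-based value is 80.6%. Protocol 8.2.1 states 80%.

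**Effect of adjustment.** Replace SD by SD × √(1 − R²). The half-width is 1.96 × SE. The last column is the weakest cell of SAP Table 2 (SD 1.5, difference −0.4 %/year).

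| Assumed R² | Interval width, relative | Half-width, combined (%/yr) | Power, combined | Power, per gender | Power, weakest cell |
|---|---|---|---|---|---|
| 0 | 1.000 | 0.340 | 98.1% | 81.3% | 84.9% |
| 0.02 | 0.990 | 0.337 | 98.3% | 82.1% | 85.6% |
| 0.05 | 0.975 | 0.332 | 98.5% | 83.2% | 86.7% |
| 0.10 | 0.949 | 0.323 | 98.9% | 85.2% | 88.4% |
| 0.20 | 0.894 | 0.305 | 99.5% | 89.0% | 91.7% |

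For R² between 0.02 and 0.10, the gain is 0.2–0.8 points in the combined analysis and 0.8–3.9 points per gender.

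**Limits of this check.** It treats the annualised difference as a simple two-sample mean, as the plan's own power figures do. The actual estimator (SAP 7.1.5.1) averages six visit estimates, each divided by its time in years. Their relative weights are 2, 1, 0.667, 0.5, 0.4 and 0.333, which sum to 4.9, so the six-month visit carries 2/4.9 = 41%. A factor that acts on the rate of loss has an effect that grows with time. One constant coefficient fits that poorly, so the table may overstate what plain main effects deliver.

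**The case against.** The strongest case against is that this is a preference among acceptable models. The model already holds baseline BMD, BMI, age and the stratification factor. Neither document gives an R² or says how strongly either factor predicts BMD change. Nor do they say whether the SD of 1.3 %/year is already covariate-adjusted. If it is not, part of the available precision comes from the present covariates, and the further gain in power is smaller. The benefit to the primary test is negligible. All of this stands. It limits the size of the point but does not show that adjustment would do harm.

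A reader might also infer more than the documents support:

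- **That the omission biases the result.** It does not. Randomisation protects the comparison with or without these terms.
- **That smoking is ignored.** The SAP plans to examine it by interaction and, if triggered, by split models. It is only the main estimate that is not adjusted for it.
- **That baseline bone medication is equally available.** Protocol 5.6 gives no look-back for non-COPD drugs, and the planned tables of BMD medication (1.24 and 1.25) cover on- and post-treatment use. The pre-treatment phase appears only in a listing, so a baseline value is plausible but only indirectly supported.
- **That the case rests on prior steroid users coming off a steroid on VI and returning to one on FF/VI.** That describes a treatment effect differing by prior use, which a main effect does not address.
- **That adjustment is needed to make missing-at-random credible.** The SAP states that assumption for sporadic missed visits (7.1.4), and no passage suggests that prior users withdraw at different rates by arm.

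Finally, a 30-day look-back is a crude measure of steroid exposure for bone. Smoking status is the firmer of the two candidates.

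**Conclusion.** The point holds as an optional efficiency improvement. Two recorded baseline factors, one of them named by the SAP as of interest, are absent from the models behind the primary and key secondary results. On an assumed R² of 0.02–0.10, the interval narrows by 1–5%, combined power gains less than one point on 98.1%, and per-gender power rises from 81.3% to 82.1–85.2%. These figures rest on the plan's SD being the residual SD under the present model, on the two-sample simplification, and on an R² for which the documents offer no value. The validity of the planned comparison is not in question.

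A related gap does not depend on R². The protocol requires added covariates to be settled in advance, and SAP 5.4.1 leaves the list open.

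**What to change.** Before unblinding:

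1. Add smoking status at screening (current/former) as a main effect in the hip and spine models, overall and by gender.
2. Add inhaled-steroid use in the 30 days before Visit 0 (yes/no) in the same way.
3. Decide whether each should also have a by-visit term, as log baseline BMD does, and write the decision down.
4. Add baseline bone medication only if a pre-randomisation yes/no value can be derived from recorded start dates. Do not use on-study bone medication: it arises after randomisation, and SAP 7.1.4 treats it as an intercurrent event.
5. Extend the observed-margins dataset in SAP 7.1.5.1 to the new terms.
6. Replace the open sentence in SAP 5.4.1 with the final list, and record the change in SAP Table 1, where the addition of age is already noted.

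No new data are needed for items 1 and 2. The cost is two parameters as main effects, or 2 × 6 = 12 if each factor has its own coefficient at all six visits, plus a little programming.

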#### Estimates:

- The estimates of the mean and difference for each treatment group from the model will be exponentiated to produce ratios. This will then be presented as a percentage change in BMD per year with 95% confidence intervals.
   I.e. percentage change = (exp(estimate)-1)\*100.
- In addition, these percent changes will be converted to annual percent changes by dividing by the year. E.g. the 1.5 year visit annual percent change will be calculated as (exp(estimate/1.5)-1)\*100
- For the treatment difference, this will be presented as a percent difference in change in BMD per year with 95% confidence interval. I.e. difference = [exp(log\_estimate for FF/VI log\_estimate for VI)-1]\*100. In addition, the difference will be converted to annual percent difference as explained above.

- The estimates of the percent change in BMD and the percent change per year by treatment arm and the treatment difference will be presented at each 6 monthly analysis visit to check for consistency.
- These 6 monthly estimates will be averaged (see diagram below) to calculate the overall treatment estimates and the treatment difference, which will be used for the primary test of non-inferiority.
- The calculation would be: Overall estimate of percentage change in BMD per year = (a/0.5 + b/1 + c/1.5 + d/2 +e/2.5 + f/3) / 6, where a to f are the estimates at each 6 monthly post-baseline analysis visit.

#### **Model Structure:**

- The variance-covariance matrix will be assumed unstructured.
- Kenward Roger (KR) method will be used for calculating degrees of freedom. If the analysis
  does not run using the KR method then the residual method will be used instead.
- An observed margins (OM) dataset will be used to derive the LS means using coefficients
  which are based on the subjects used in the analysis. This is a dataset with a row for every
  subject-visit combination that contains all of the covariates. The OM will be at the average
  logarithm of baseline BMD, the average baseline age and the average baseline BMI.

#### Covariates to be investigated:

 Treatment\*Covariate interactions will be included in the model individually. If these are significant at the 10% level then a model split by the covariate of interest will be investigated.

#### **Model Checking & Diagnostics**

Distributional assumptions underlying the model used for analysis will be examined by
obtaining a normal probability plot of the residuals and a plot of the residuals versus the fitted
values (i.e. checking the normality assumption and constant variance assumption of the model
respectively) to gain confidence that the model assumptions are reasonable.

